6 STUDY TREATMENT

6.1 Study Treatment(s) Administered

6.1.1 Investigational Products

Details for RXC004 and denosumab, which will be administered in all Modules, are provided in Table 10. Details for pembrolizumab, which will be administered in Module 3 only, are provided in Section 12.7.

Table 10 Investigational Products

Treatment	RXC004	Denosumab
Module	Module 1, 2 and 3	Module 1, 2 and 3
Type	Drug	Biologic
Dose Formulation	0.5mg or 1mg capsules	Ampule
Dosage Level(s)	
• 1 mg QD (Cohort 2, Module 2)• 1.5 mg QD (Module 3)• 2 mg QD (Module 1, and Cohort 1, Module 2)	120 mg once every month
Route of Administration	Oral	SC injection
Use	Experimental	Prophylactic
IMP and NIMP	IMP	IMP
Sourcing	Provided centrally by the Sponsor	Provided centrally by the Sponsor
Packaging and Labelling	RXC004 will be provided in white 50 mL HDPE Duma bottles. Each bottle will be labelled as required per country requirement	Study Intervention will be provided in a vial containing 120 mg in a 1.7 mL solution. Each vial will be labelled as required per country requirement

HDPE, high-density polyethylene; IMP, investigational medicinal product; NIMP, non-investigational medicinal product; QD, once daily; SC, subcutaneous.

6.2 Preparation/Handling/Storage/Accountability of Study Treatments

Details for RXC004 and denosumab are provided below. For pembrolizumab (applicable to Module 3 only), see Section 12.7.2.

6.2.1 RXC004

RXC004 will be supplied by Redx as 0.5 mg and 1.0 mg capsules. A complete description of the chemistry and formulation may be found in the Investigational Medicinal Product Dossier. The Quality Control Standards and requirements for RXC004 study medication are described in separate release protocols/ Certificate of Analysis.

RXC004 is formulated as two dosage strengths capsules manufactured by Quay Pharma, [name]. The RXC004 capsules strengths are 0.5 mg and 1.0 mg for oral administration. Stability testing of RXC004 is ongoing. Please

refer to the current IMP label for the Expiry Date associated with the current shelf-life of the product.

Patients must fast (water to drink only) for at least 2 hours prior to taking a dose to at least 1 hour post-dose for all doses.

6.2.2 Denosumab

Denosumab is a human monoclonal antibody (IgG2) that targets and binds with high affinity specifically to RANKL, preventing RANKL/RANK interaction from occurring and resulting in reduced osteoclast numbers and function, thereby decreasing bone resorption and cancer-induced bone destruction.

Denosumab (XGEVA[®]) is approved administered at 120 mg SC once monthly for use in the prevention of skeletal-related events in patients with advanced cancers with bone metastases.

The use of denosumab in this trial is outside labelled use as patients may not have bone metastases. The rationale for its prophylactic use in all patients is as a bone-protection measure based on the increased risk of bone fragility with RXC004 treatment.

6.3 Study Treatment Compliance

The first dose of RXC004 will be taken at site under medical supervision. The date, and time of dose administered at site will be recorded in the source documents and recorded in the eCRF. When patients self-administer RXC004 at home, compliance with study treatment will be assessed at each visit. Compliance will be assessed by collection of a patient diary cards and counting of returned capsules, during the site visits and documented in the source documents and eCRF. Deviation(s) from the prescribed dosage regimen should be recorded in the eCRF.

A record of the number of RXC004 capsules dispensed to and taken by each participant must be maintained and reconciled with study treatment and compliance records. Treatment start and stop dates, including dates for treatment delays and/or dose reductions will also be recorded in the eCRF.

Details for pembrolizumab (Module 3) are provided in Section 12.7.3.

6.4 Reporting of Concomitant Therapy

Any medication or vaccine (including over-the-counter or prescription medicines, vitamins, and/or herbal supplements) that the participant is receiving at the time of enrolment or receives during the study must be recorded along with:

- Reason for use
- Dates of administration including start and end dates

- Dosage information including dose and frequency

Concomitant medication may be given as medically indicated with the exception of prohibited concomitant medication (Section 5.6.3 and Appendix E).

The timeframe for reporting concomitant therapy is from Screening (within 28 days prior to first dose of study treatment) up to 30 days after last dose of RXC004, and up to 90 days after last dose of pembrolizumab in Module 3. The Medical Monitor should be contacted if there are any questions regarding concomitant or prior therapy.

6.5 Dose Modification

Dose modifications and stopping criteria for RXC004 are detailed in Section 6.5.1.

For participants in Module 3 (RXC004 in combination with pembrolizumab): Dose modifications and stopping criteria for pembrolizumab are detailed in Appendix L. If either agent is interrupted or discontinued for a related AE, the other agent (pembrolizumab or RXC004) may be continued if the patient is judged (by the investigator) to be receiving clinical benefit.

6.5.1 Dose Modifications for RXC004

RXC004 dose reduction and interruption are permitted.

RXC004 may be dose interrupted (withheld) until a clinically significant (any grade) and/or a grade ≥ 3 related adverse event resolves to baseline or \leq grade 2. RXC004 may also be withheld if it is necessary to give a concomitant medication that is a moderate or strong CYP3A4 inhibitor.

Colitis events may occur with RXC004 or with pembrolizumab, and should be managed per Appendix K and, for participants in Module 3, the dose modification and toxicity management guidelines for irAEs associated with pembrolizumab (Appendix L 1) if applicable. For patients receiving the combination treatment with RXC004 and pembrolizumab, the most conservative guideline should be followed.

RXC004 dose interruption and stopping criteria are detailed in Table 11.

Table 11 RXC004 Dose Modification and Stopping Criteria

Event	Action
Colitis events (e.g. Colitis, ileitis, enterocolitis etc)	
Grade 1	Reduce RXC004 to a lower dose (see Table 12 for dose reduction scheme) and manage per Appendix K. If receiving RXC004 in combination with pembrolizumab, no additional action is required for pembrolizumab.
Grade 2	Interrupt RXC004. Manage as per Appendix K. When event has resolved to Grade $\leq 1^a$ and steroids have been tapered to prednisolone ≤ 10 mg per day (or equivalent), resume RXC004 at a lower dose (see Table 12 for dose-reduction scheme). If event recurs after re-starting study treatment, then RXC004 should be permanently discontinued. If receiving RXC004 in combination with pembrolizumab, interrupt pembrolizumab and see Appendix L for guidance.
Grade 3	Interrupt RXC004. Manage as per Appendix K. When event has resolved to Grade $\leq 1^a$ and steroids have been tapered to ≤ 10 mg of prednisolone per day (or equivalent), resume RXC004 at a lower dose (see Table 12 for dose reduction scheme). If event recurs after re-starting study treatment, then RXC004 should be permanently discontinued. If receiving RXC004 in combination with pembrolizumab; permanently discontinue both agents and manage as per Appendix K and Appendix L.
Grade 4	If receiving RXC004, either as monotherapy or in combination with pembrolizumab: Permanently discontinue both agents. Manage per Appendix K and Appendix L.
Dysgeusia events	
Grade 1/2	RXC004 related: Manage per Appendix J Consider dose reduction, depending on clinical symptoms Interrupt RXC004 treatment if dysgeusia is associated with >5 kg weight loss from baseline.

Table 11 RXC004 Dose Modification and Stopping Criteria

Event	Action
Grade 2 associated with a 10-20% decrease in body weight	RXC004 related: Manage per Appendix J Reduce RXC004 to a lower dose (see Table 12 for dose-reduction scheme).
Grade 2 associated with a > 20% decrease in body weight	RXC004 related: Permanently discontinue RXC004. If receiving RXC004 in combination with pembrolizumab, the pembrolizumab can continue if clinical benefit is judged by the Investigator.
Other AEs	
RXC004-related Grade 3 toxicity (1st event)	Interrupt RXC004 and provide supportive care, resume a lower dose level when resolved (\leq Grade 2 or returns to baseline). See Table 12 for dose-reduction scheme.
RXC004-related Grade 3 toxicity (subsequent repeat of a previously experienced event)	Permanently discontinue the related study treatment
Any Grade 4 toxicity	Permanently discontinue the study treatment.
All Grade events	Study treatment can be interrupted or discontinued for any clinically significant AEs that in the investigator's opinion warrants treatment interruption or discontinuation.
Bone events	
Confirmed (by imaging) RXC004-related fragility bone fracture (excluding grade 1 vertebral deformities)	Permanently discontinue RXC004. Pembrolizumab can continue if the patient is receiving clinical benefit as judged by the investigator.
Patients with a DEXA scan showing >7% worsening in BMD at lumbar spine or total hip compared to baseline	Permanently discontinue RXC004. Pembrolizumab can continue if the patient is receiving clinical benefit as judged by the investigator.
An individual increase in β -CTX of CCI from the baseline (screening) value or an individual measurement of CCI	Permanently discontinue RXC004 unless the patient has received clinical benefit (investigator assessment) and continued treatment is warranted. Pembrolizumab treatment can continue if the patient is receiving clinical benefit as judged by the investigator.
COVID-19 infection	
Positive COVID-19 test	Interrupt RXC004, until acute symptoms have resolved.

Table 11 RXC004 Dose Modification and Stopping Criteria

Event	Action
Major surgery	Interrupt RXC004, resume at full dose. Pembrolizumab does not need to be interrupted. No stoppage is required for biopsy procedures.
Vomiting	If vomiting occurs shortly after RXC004 is swallowed, the dose may be replaced if all of the intact capsules can be counted. Resume with the following scheduled dose.
Missed RXC004 dose	Allowed to take the scheduled dose up to 4 hours after the scheduled dose time. If greater than 4 hours, the missed dose should not be taken and patient should continue with next dose at allotted time.

^a Attempts should be made to confirm that the colitis has resolved to Grade ≤ 1 (e.g. normalised CRP or fecal calprotectin if raised during event; GI appearance normalised on X-ray/CT or endoscopy) before restarting RXC004.

AE, adverse event; BMD, bone mineral density; COVID-19, Coronavirus disease 2019; QD, once daily.

Toxicity will be assessed using the NCI Common Terminology Criteria for Adverse Event (CTCAE) version 5.0, unless otherwise specified. Every effort should be made to administer trial treatment at the planned dose and schedule. However, patients experiencing RXC004-related toxicities may have their RXC004 dose modified as outlined below.

RXC004 related toxicities observed during the course of the study will be managed by interruption of RXC004 and initiation of appropriate treatment as judged by the Investigator. Upon re-starting treatment the guidance for dose reduction in RXC004 contained in Table 12 should be followed.

Table 12 Guidance for Dose Reductions for RXC004-related Adverse Events

Dose Level	RXC004 (Module 1 and Module 2, Cohort 1 only)	RXC004 (Module 3 only)	RXC004 (Module 2, Cohort 2 only)
Initial dose level	2 mg QD	1.5 mg QD	1 mg QD
1st dose reduction			
• Grade 3 toxicity (1 st event)	Hold RXC004 ^b . Upon resolution to ≤ Grade 2, restart at 1.5 mg QD	Hold RXC004 ^b . Upon resolution to ≤ Grade 2, restart at 1 mg QD	Hold RXC004 ^b . Upon resolution to ≤ Grade 2, restart at 0.5 mg QD
• Grade 1/2 dysgeusia ^a	Dose reduce to 1.5 mg QD	Dose reduce to 1 mg QD	Dose reduce to 0.5 mg QD
2nd dose reduction			
• Grade 3 toxicity (1 st unique event)	Hold RXC004 ^b . Upon resolution to ≤ grade 2, restart at 1 mg QD	Hold RXC004 ^b . Upon resolution to ≤ Grade 2, restart at 0.5 mg QD	Not permitted. Permanently discontinue RXC004.
• Grade 3 toxicity (recurrence of a previously experienced Grade 3 event)	Not permitted. Permanently discontinue RXC004	Not permitted. Permanently discontinue RXC004	Not permitted. Permanently discontinue RXC004
• Grade 2 dysgeusia associated with > 20% weight loss ^a	Not permitted. Permanently discontinue RXC004	Not permitted. Permanently discontinue RXC004	Not permitted. Permanently discontinue RXC004.
3rd dose reduction			
	Not permitted. Permanently discontinue RXC004.	Not permitted. Permanently discontinue RXC004.	Not applicable

^a Dependent on clinical symptoms, excluding other possible causes and despite optimal treatment.

^b RXC004 can be resumed after an interruption, as long as no other treatment discontinuation criteria have been met. Patients who experience disease progression while QD, once daily.

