RXC004 has not shown the potential to induce or inhibit CYP enzymes or transporters at the dose to be investigated in this study but it is exclusively metabolised by CYP3A4 and as such has the potential for DDI with potent CYP inhibitors (which could increase levels of RXC004, leading to a higher risk of AEs). As such, strong and moderate CYP3A4 inhibitors are contraindicated in this protocol (see Appendix E). Patients with pancreatic and biliary tract cancers commonly require co-medications with analgesics, antacids, antibiotics, anti-emetics, anti-diabetic agents, anti-diarrhoeal drugs, anti-depressants, anxiolytic drugs, pancreatic enzyme replacements and other nutritional supplements. Some agents within these classes are CYP3A4 inhibitors.

Appendix E highlights the CYP 3A4 inhibitors which are also likely to be commonly used in CRC patients. These drugs should be avoided, and alternatives used wherever possible. If it is

not possible to use an alternative (e.g. if a specific antibiotic or anti-fungal treatment is needed), RXC004 should be interrupted.

Potential for QTc Prolongation

Based on pre-clinical data (hERG assay, ECG monitoring in 28-day GLP toxicology studies), RXC004 is not considered to have a significant potential to prolong the QTc interval. RXC004 did not lead to cardiac AEs including arrhythmias, or syncope in the Phase 1 study.

TriPLICATE ECGs will be collected in this other RXC004 studies so that the potential for QTc prolongation can be explored in future as part of a population PK analysis.

Potential for an Effect of Food on RXC004 Exposure

It is not yet known whether food may increase or decrease the exposure of RXC004. Until such data are generated, RXC004 must be given in a fasted state, as described in Section 5.6.2, and this is explained to patients in the Information Sheet.

Potential for Risks in Specific Patient Populations

A preliminary analysis of data from the Phase 1 study showed no effect of age, sex, BMI or race on RXC004 PK.

Pre-clinical development showed that RXC004 is exclusively metabolised by CYP3A4 and there was no renal clearance of RXC004. However, there is currently no information on the clearance of potential human metabolites of RXC004. While data are limited, the study inclusion criteria will restrict the use of RXC004 to patients with adequate renal and hepatic function.

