5.6.2 Meals and Dietary Restrictions

Patients must fast (water to drink only) from at least 2 hours prior to taking a dose to at least 1-hour post-dose for all doses. Patients should abstain from eating large amounts of grapefruit and Seville oranges (and other products containing these fruits e.g. grapefruit juice or marmalade) during the study (e.g., no more than a small glass of grapefruit juice (120 mL) or half a grapefruit or 1-2 teaspoons (15g) of Seville orange marmalade daily).

For participants in Module 3, no additional meal or dietary restrictions are required with regard to pembrolizumab study treatment, unless modifications are required to manage an AE such as diarrhoea, nausea, or vomiting.

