5.6.3 Concomitant Treatments

5.6.3.1 Prohibited and Restricted Medications (Modules 1, 2, and 3)

Medications or vaccinations specifically prohibited in the exclusion criteria are not allowed during the ongoing trial. If there is a clinical indication for any medication or vaccination specifically prohibited during the trial, discontinuation from study intervention or vaccination may be required. The investigator is to discuss prohibited medication/vaccination with the Sponsor's Clinical Director. The final decision on any supportive therapy or vaccination rests with the investigator and/or the participant's primary physician. However, the decision to continue the participant on study treatment requires the mutual agreement of the investigator, the Sponsor, and the participant.

The following concomitant medication is prohibited:

1. The use of any natural/herbal products or other 'folk remedies'.
2. No other chemotherapy, or other anticancer therapy, including radiation therapy (except local treatment to a symptomatic solitary lesion), immunotherapy, and hormonal therapy (contraception and hormone replacement therapy is acceptable), or other investigational product is permitted other than the study treatments.
3. The use of some CYP3A4 inhibitors and inducers should be restricted prior to first dose of study treatment and throughout the study treatment, as RXC004 is observed to be exclusively metabolised by CYP3A4. For a list of prohibited CYP3A4 inhibitors and inducers and details of restrictions prior to the first dose of study treatment, please refer to Appendix E.

4. Drugs that are immunosuppressive or may cause secondary osteoporosis should not be administered (e.g. corticosteroids, pioglitazone or rosiglitazone). The following exceptions are allowed:
 - Use of immunosuppressive medication for the management of colitis events (per Appendix K), or pembrolizumab-related AEs (please refer to Appendix L).
 - Steroids required for the management of RXC004- or pembrolizumab-related AEs should be tapered to prednisolone \leq 10 mg/day equivalent, before re-starting study treatment.
 - Systemic glucocorticoids when used for the following purposes:
 - To modulate symptoms of an AE that is suspected to have an immunologic aetiology
 - For the prevention of emesis
 - To premedicate for IV contrast allergies
 - To treat chronic obstructive pulmonary disease (COPD) exacerbations (only short-term oral or IV use in doses $>$ 10 mg/day prednisone equivalent)

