Appendix E Prohibited CYP3A4 Inhibitors and Inducers

CYP 3A4 Inhibitors [Bold text denotes commonly used co-medications in patients with pancreatic or biliary tract cancers]	CYP 3A4 Inducers [None of these drugs are commonly used co-medications in patients with pancreatic or biliary tract cancers]

Strong CYP 3A4 Inhibitors Concomitant use of these drugs has the potential to increase the exposure of RXC004 >5-fold These agents must not be given within 14 days of first dose of study treatment
 
Boceprevir, cobicistat, danoprevir and ritonavir, elvitegravir and ritonavir, grapefruit juice, indinavir and ritonavir, itraconazole, ketoconazole, lopinavir and ritonavir, paritaprevir and ritonavir and (ombitasvir and/or dasabuvir), posaconazole, ritonavir, saquinavir and ritonavir, telaprevir, tipranavir and ritonavir, troleandomycin, voriconazole, clarithromycin, idelalisib, nefazodone, nelfinavir.
	
Strong CYP 3A4 Inducers Concomitant use of these drugs has the potential to decrease the exposure of RXC004 by >80% These agents must not be given within 14 days of first dose of study treatment
 
Aptalutamide, carbamazepine, enzalutamide, mitotane, phenytoin, rifampin, St. John's wort.

Moderate CYP3A4 Inhibitors Concomitant use of these drugs has the potential to increase the exposure of RXC004 by 2-5-fold A washout period of 14 days is recommended and a minimum washout period of 5 half-lives (See SMPC or USPI) is required before first dose of study treatment.
 
Aprepitant, , conivaptan, crizotinib, cyclosporine, diltiazem, dronedarone, erythromycin, fluconazole, fluvoxamine, imatinib, tosipam, verapamil lansoprazole.
	
Moderate CYP 3A4 Inducers Concomitant use of these drugs has the potential to decrease the exposure of RXC004 by 60-80% A washout period of 14 days is recommended and a minimum washout period of 5 half-lives (See SMPC or USPI) is required before first dose of study treatment.
 
Bosentan, efavirenz, etravirine, phenobarbital, primidone.

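### For an unavoidable moderate or strong CYP3A4 inhibitor, Protocol Section 2.3.1.2 directs that RXC004 be interrupted, but Section 6.5.1 only permits it and Table 11 has no matching row

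*Protocol*

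**What the plan says.** All references are to the Protocol.

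- **Section 2.3.1.2** contraindicates strong and moderate CYP3A4 inhibitors. For the case where it is "not possible to use an alternative (e.g. if a specific antibiotic or anti-fungal treatment is needed), RXC004 should be interrupted", the instruction is a directive.
- **Section 6.5.1** covers the same case in permissive terms: "RXC004 may also be withheld if it is necessary to give a concomitant medication that is a moderate or strong CYP3A4 inhibitor". It names Table 11 as the place for interruption and stopping criteria.
- **Table 11** covers colitis, dysgeusia, other adverse events, bone events, COVID-19, major surgery, vomiting and missed doses. It has no CYP3A4 row. **Table 12** deals only with RXC004-related adverse events.
- **Section 6.4** sets the general bar: "Concomitant medication may be given as medically indicated with the exception of prohibited concomitant medication (Section 5.6.3 and Appendix E").
- **Section 5.6.3.1** restricts these drugs before and during treatment. If a prohibited drug is clinically indicated, the investigator discusses it with the Sponsor, discontinuation may be required, and "the decision to continue the participant on study treatment requires the mutual agreement of the investigator, the Sponsor, and the participant".
- **Restart:** Table 12, footnote b, says "RXC004 can be resumed after an interruption, as long as no other treatment discontinuation criteria have been met". The Appendix E washouts are worded for the first dose only. For moderate inhibitors 14 days is recommended and "a minimum washout period of 5 half-lives (See SMPC or USPI) is required before first dose of study treatment". Strong inhibitors are barred within 14 days of the first dose, with no half-life alternative.

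**The concern.** The directive stands in a background risk narrative and the permissive wording stands in the operative dosing section. Section 6.5.1 also asks for every effort to keep to the planned dose and schedule. A site working from that section could take holding RXC004 to be optional and co-dose.

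That matters because the protocol states that RXC004 is metabolised exclusively by CYP3A4. It also says that these patients commonly need drug classes, such as antibiotics, antacids and anti-emetics, in which some agents are inhibitors. Appendix K is one route in the monotherapy modules. During the steroid taper for Grade 3 colitis it asks sites to consider prophylactic antibiotics and anti-fungals, and it then allows RXC004 to restart at a lower dose. Appendix E lists fluconazole and erythromycin as moderate inhibitors, and itraconazole, posaconazole, voriconazole and clarithromycin as strong.

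The stake is overexposure in a patient whose usual dose is not far below a non-tolerated one. No endpoint, sample size or analysis is affected.

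**Working it through.** **1. Is it the same situation?** Yes. Both sections address an inhibitor that has to be given. In Section 2.3.1.2 the drugs to be avoided are, grammatically, those highlighted in Appendix E, but the paragraph before contraindicates strong and moderate inhibitors as a class. One section says *should*, the other *may*.

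**2. Does anything else in Section 6.5.1 supply the directive?** The sentence before the CYP3A4 sentence also uses *may*, for Grade 3 or higher related events. For Grade 3 events Table 11 then gives a firm instruction to interrupt, and for Grade 4 to discontinue. Major surgery, which is not an adverse event, also has a firm row. The CYP3A4 ground has none. The COVID-19 row ("Interrupt RXC004, until acute symptoms have resolved") is firm too, but Section 8.3.11 makes COVID-19 infection an adverse event, so it is not a second non-adverse-event comparator.

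**3. Could co-dosing matter?** The documents state no figure for this, so it is a plausibility check only. Inputs are the steady-state geometric means in Table 9 and the potential fold increases in Appendix E (moderate 2 to 5, strong above 5). The reference is the non-tolerated 3 mg dose: AUC0-24 2340 h·ng/mL (CV 32.5%, n=4).

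Fold needed to reach the 3 mg AUC = 2340 / AUC at the assigned dose:

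- 2 mg: 2340/931 = 2.51 (n=4, CV 61.1%)
- 1.5 mg in combination: 2340/706 = 3.31 (n=5, CV 40.1%; nivolumab data as proxy for pembrolizumab)
- 1 mg: 2340/392 = 5.97 (n=3)

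The first two lie inside the moderate range. At 1 mg, even a 5-fold rise gives 392 × 5 = 1960, below 2340, so on point estimates only a strong inhibitor could reach it.

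Approximate 95% intervals use a Welch t on the log scale with log SD = √ln(1+CV²). They assume that Table 9's %CV is the geometric CV and that AUC is log-normal.

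- 2 mg: log SDs 0.563 and 0.317, SE 0.323, df 4.7, t 2.62; exp(ln 2.51 ± 2.62 × 0.323) = 1.08 to 5.85
- 1.5 mg in combination: log SDs 0.386 and 0.317, SE 0.234, df 7.0, t 2.37; 1.90 to 5.77

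Other measures vary. On Cmax: 220/68.5 = 3.2 (2 mg) and 220/76.4 = 2.9 (1.5 mg combination). On Cmin: 73.1/26.8 = 2.7 (2 mg, interval about 0.6 to 12.5) and 73.1/13.6 = 5.4 (1.5 mg combination), the last above the moderate range.

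**4. What was seen at those exposures?** Intestinal inflammation occurred in 0 of 20 Phase 1 patients starting at 2 mg or below (Clopper-Pearson 95% 0 to 16.8%) and in 3 of 4 at 3 mg (19.4 to 99.4%). In Phase 2 there were two Grade 3 SAEs in 12 + 21 = 33 patients dosed, 6.1% (0.7 to 20.2%), both at 2 mg. The 3 mg events arose under continuous dosing. Both Grade 2 colitis events presented in Cycle 2. Table 1 does not mark the Grade 3 enteritis as starting outside the DLT window, which ended on Cycle 1 Day 21.

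**The case against.** The best reply is that *may* in Section 6.5.1 lists permitted grounds for an interruption. The section opens by saying that interruptions are allowed, and Section 2.3.1.2 supplies the directive, so the two can be read together. Harm then needs a site to read Section 6.5.1 in isolation, past the bar in Section 6.4 and the Sponsor discussion and three-way agreement in Section 5.6.3.1.

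Much of this stands. These are real safeguards, and the two sentences are not opposite instructions. It does not close the gap. For Grade 3 adverse events the firm instruction is in Table 11, whereas for CYP3A4 inhibitors nothing in Section 6.5.1 provides one. Section 5.6.3.1 governs whether treatment continues, without saying that continuing excludes co-dosing.

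The objection to materiality also largely stands. The 2 mg AUC interval spans the whole moderate range, so a point estimate inside that range shows little, and the 2 mg Cmin interval includes no difference. A reader might infer that co-dosing would reproduce the 3 mg toxicity, or that the Phase 2 SAEs reflect inhibitor use. The documents support neither. Appendix E speaks only of a potential increase, the 3 mg events followed continuous dosing, and no inhibitor is linked to the two SAEs.

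**Conclusion.** The inconsistency is in the current text and is worth correcting, as a minor safety-wording matter. It is a directive in one section against a permission in another, and the operative section and its table lack the directive. A reader might go further and say that the protocol authorises co-dosing. It does not: the drugs are prohibited and continuing needs Sponsor agreement. Co-dosing is merely not excluded where sites look up dosing.

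The size is a plausible rise towards 3 mg exposure, about 2.5-fold from 2 mg and 3.3-fold from 1.5 mg in combination on AUC. This rests on 4 to 5 patients per dose, on nivolumab data standing in for pembrolizumab, and on the log-normal assumption above. The risk from a short course, the risk from restarting soon after the inhibitor stops, and the number of patients affected are all unknown. The RXC004 half-life is redacted and no inhibitor half-lives are given.

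**What to change.** In Section 6.5.1, replace the permissive verb with the directive in Section 2.3.1.2, so that RXC004 should be interrupted. Add a Table 11 row: interrupt RXC004 while a concomitant moderate or strong CYP3A4 inhibitor is given. Limit the row to medications, so that it does not collide with the dietary allowance in Section 5.6.2 ("no more than a small glass of grapefruit juice (120 mL) or half a grapefruit"), since Appendix E lists grapefruit juice among strong inhibitors.

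A restart interval is optional. If one is added, it should mirror Appendix E by class:

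- **Moderate:** at least 5 inhibitor half-lives (0.5⁵ = 3.1% remaining), with 14 days recommended.
- **Strong:** 14 days, with any shorter interval only by agreement with the Medical Monitor. Applying 5 half-lives to strong inhibitors could be looser than the protocol's own pre-dose rule.

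The cost is one wording change and one table row in an amendment, with no new procedures or patients. The downside is extra missed RXC004 doses in the few patients affected. A 14-day hold after the inhibitor stops is 14/21 = 67% of a cycle. Against the second-line PFS quoted in the protocol (1.5 to 4 months across the two tumour types, at 30.4375 days per month), it is 14/45.7 = 31% down to 14/121.75 = 11%. A patient on hold at progression would also not qualify for treatment beyond progression under Section 7.1.1.
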